Study Protocol

Adherence to HIV Treatment Postpartum: The Implications of Transitions Among Women Living with HIV in South Africa

ClinicalTrials.gov #: NCT04846569

Version 5.0

November 5, 2021

IRB Federalwide Assurance Numbers:

- FWA00004460 (Brown University)
- FWA00001637 (University of Cape Town)

Study Sponsor: National Institute of Mental Health (K01MH112443)

Protocol Summary

Adherence to HIV Treatment Postpartum: The Implications of Transitions Among Women Living with HIV in South Africa

Study Aims:

Aim 1: Identify contextual, interpersonal, clinic, and individual-level factors that influence women's HIV treatment adherence during periods of key points of transition during pregnancy and postpartum, using longitudinal in-depth qualitative interviews among a cohort of pregnant women (N=25-30) following them up to 12 months postpartum.

Aim 2: Evaluate the feasibility and preliminary efficacy of a Transition Theory-based ART adherence intervention for postpartum women living with HIV, using a small scale randomized controlled trial (RCT; N=60).

Aim 3: Assess participants' experiences of the intervention, perceived usefulness, and identify ways to refine the intervention for future evaluation, using in-depth individual interviews will be conducted with all participants in the intervention condition after follow-up assessments have been completed.

Sample size for RCT: 62 participants consented; 43 randomized

Study population: Adult (≥ 18 years), HIV-positive, pregnant (23-34 weeks) women attending antenatal services at the study site, prescribed ARVs

Participating site: Gugulethu Midwife Obstetric Unit, Cape Town, South Africa

Study design: Small-scale two-arm randomized control trial, assessing feasibility and preliminary efficacy.

Study timeline for RCT: April 2021-December 2022

Principal Investigator:

[name]
Assistant Professor of Behavioral and Social Sciences
International Health Institute
Brown University School of Public Health
[name]
[name]
[name]
[contact]

Co-Investigators/K01 Mentors:

[name], PhD

Professor of Epidemiology and Biostatistics
School of Public Health and Family Medicine
University of Cape Town
Cape Town, South Africa
[name]
[contact]

[name]
Professor, Behavioral and Social Sciences
Brown University School of Public Health
[name]
[name]
[contact]
[contact]

[name]
Associate Professor, Epidemiology

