1. Adherence self-efficacy - confidence in taking medications: Adherence self-efficacy will be measured using the AACTG adherence self-efficacy scale, 15 items, using 5 point Likert scale ranging from not confident at all to very confident. Total scores range from 15-75, with higher scores indicating higher self-efficacy.

2. Acceptability/Utility of the Intervention: Acceptability of the Transition Theory-based intervention, assessed during in-depth interviews among participants in the intervention condition to gauge general feelings of acceptability and perceived usefulness of the intervention.

3. Study Design

Overview

We propose to address these objectives using a two phase design in which we identify how influential factors change during key moments of transition during pregnancy and postpartum and to construct an intervention that effectively addresses these moments of transition to bolster ART adherence and engagement in care for mothers living with HIV.

Phase 1 (Aim 1)

Phase 1 involved a longitudinal qualitative cohort design with interviews with 30 pregnant and postpartum women at 4 time points to identify contextual, interpersonal, clinic, and individual-level factors that influence women's HIV treatment adherence during periods of key points of transition during pregnancy and postpartum. (HREC 344/2017)

Phase 2 (Aims 2 & 3)

Aim 2: Evaluate the feasibility and preliminary efficacy of a Transition Theory-based ART adherence intervention for postpartum women living with HIV

Informed by Aim 1, this intervention will be tested using an open pilot (n=5) and a small scale randomized controlled trial (RCT; n=60 to complete baseline). The purpose of the open pilot is to pretest all study procedures, particularly recruitment and retention, to increase the feasibility of the RCT, as well as to pilot test the intervention content. Primary hypothesis if the RCT: The intervention will be feasible to conduct with postpartum women living with HIV in Cape Town, South Africa. Secondary hypothesis: Postpartum women in the intervention condition will have better ART adherence than women in the control condition at follow-up.

For the RCT, pregnant women living with HIV (n=60 to complete baseline; up to n=100 will be approached) will be approached to participate. Following informed consent, women will complete an enrollment study visit and will then be randomized to one of two arms:

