- Arm A (Transition theory-based intervention): Women randomized to this arm will receive monthly one-on-one meetings with a community health worker for four months during late pregnancy and early postpartum
- Arm B (enhanced standard of care): Women randomized to this arm will receive one meeting with a community health worker in addition to the local standard of care.

[figure not shown]
Women randomized to each arm will be asked to attend two additional assessment study visits at 3- and 6-months postpartum. The primary outcome will be self-reported ART adherence and secondary outcomes will be retention in routine HIV care (from routine electronic medical records) and HIV viral load using dried blood spots.

Participation will have no impact on any aspect of women's routine antenatal and obstetric care during pregnancy, or on any aspect of their postpartum care. In addition, participation will have no impact on their routine HIV care. Women randomised to the Transition intervention will receive the intervention separate from any routine medical visits. Women randomised to the enhanced standard of care will attend all routine medical visits and will receive one meeting with a community health worker separate from any routine medical visits.

Aim 3: *Assess participants' experiences of the intervention, perceived usefulness, and identify ways to refine the intervention for future evaluation.*

This aim will be accomplished using in-depth individual interviews with all participants who were randomized to the intervention condition after all follow-up assessments have been completed (n= up to 30)

The study schema is summarized in the diagram below:

Setting

The proposed study will take place in the community of Gugulethu in Cape Town. Aim 1 was successfully conducted in this community and our team has actively collaborated with local

health services in this setting for over 10 years. The antenatal HIV prevalence rate in Gugulethu is between 26-30%. Participants will be recruited during pregnancy from the Gugulethu Midwife Obstetrics Unit (MOU), which is a public sector facility that serves more than 4800 pregnant and postpartum women annually.

4. Study Population

For Phase 2 of this study (Aims 2 & 3), inclusion criteria are as follows:

- 18 years of age or older
- HIV positive status (based on clinic records)
- Confirmed pregnant (based on clinic records) and estimated to be 23-34 weeks gestation (clinic records or self-report)

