Following recruitment and informed consent, all participants will be assigned unique study identification numbers. Women will complete the enrolment study visit and will then be randomized to either the Transitions intervention or control (enhanced standard of care).

Randomization

Randomization will take place at the end of the enrolment study visit. Women will be randomly allocated to either the Transitions intervention or control using a 1:1 randomization scheme. Randomization numbers will be generated prior to the start of the study and will be placed in sequentially numbered opaque envelopes. Randomization envelopes will be stored in a locked cabinet in the study office at UCT and will be accessed by the project manager when a woman is fully consented and has completed the enrolment visit. Women will be informed of their random allocation at the end of the enrolment visit. Ideally, a one-on-one meeting with the CHW (first visit for those in the Transitions intervention, only visit for those in the enhanced standard of care) would occur the same day as enrolment to aid in retention. If this is not possible the CHW will contact the participant using tracing information detailed below to inform them of the date and time of the first or only one-on-one meeting.

Quantitative measures

At each study measurement visit, a trained interviewer will administer questionnaire-based measures using paper and pencil. The trained interviewer will be blinded to participants' allocation. All study measurement visits will be conducted at a space that is separate from routine care. Most measures have been used previously by our group in this setting (see references in Table of measures, below), and have been translated into isiXhosa and back-translated into English following standard procedures. An additional scale⁴⁶ developed to measure the theoretical constructs of Transition Theory has been adapted for use with women living with HIV for this study and will be translated into isiXhosa and back-translated to English prior to use in the trial.

Linkage of routinely collected clinical data

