Sample size considerations: pilot study

The overall goal of this pilot study is to determine feasibility and potential efficacy to support future larger, fully-powered tests of the intervention's efficacy. We fully acknowledge the exploratory nature of this pilot. With a sample size of 60, between two groups, 2 follow-up measurements, controlling for self-reported baseline adherence, $p=0.05$, we will have 29% power of finding a small effect (Cohen's $d=0.30$), 65% power of finding a moderate effect ($d=0.50$), and 98% power of finding a large effect ($d=0.80$). This study will be underpowered to find significant small and moderate effects however, we will be able to calculate an effect size and the direction of its impact to support a larger scale test of the intervention.

The facility that is participating in this study, the Gugulethu MOU, sees approximately 4800 pregnant and postpartum women annually, with an antenatal HIV prevalence of 28%. Thus, we do not anticipate difficulty recruiting this sample within the allotted timeframe.

Sample size considerations: In-depth Interviews (Aim 3)

We propose to interview all of the women randomized to the intervention condition ($n=$ up to 30). Based on our follow-up rates for the longitudinal qualitative cohort (HREC 344/2017), we anticipate at least an 80% retention rate at 6 months postpartum, which equates to an anticipated 24 participants completing in-depth interviews. Based on our previous experiences working with this population, we feel that 24 participants will be enough to reach saturation on key themes related to acceptability of the intervention.

Data management

The study includes data from four sources: (1) interviewer-administered questionnaires; (2) routine electronic medical records; (3) dried blood spots; and (4) IDI with participants randomized to the intervention condition. The collection of data will be conducted by (1) a fieldworker; (2) the project manager; (3) lab-based researcher; and (4) a qualitative interviewer, respectively. Procedures for data collection (regardless of source) will be outlined in SOPs. We have a bank of well-developed SOPs that our group has developed for previous studies. All data management will take place at UCT following procedures established by our group for multiple previous studies.

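### The power of 29%, 65% and 98% is stated for 60 women at baseline with no loss and no correlation given, but the same version reports 43 randomised; at 43 it is nearer 22–23%, 50–52% and 88–90%

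*Combined protocol and SAP*

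**What the plan says.** The pilot sample size paragraph in section 9 reads "With a sample size of 60, between two groups, 2 follow-up measurements, controlling for self-reported baseline adherence", at p = 0.05. It gives power of 29% for d = 0.30, 65% for d = 0.50 and 98% for d = 0.80. It does not state sidedness, the correlation between baseline and follow-up, or the correlation between the two follow-ups. It concedes low power for small and moderate effects, and gives the purpose as follows: "we will be able to calculate an effect size and the direction of its impact to support a larger scale test of the intervention".

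Section 3 (Phase 2) says what the 60 counts: "n=60 to complete baseline; up to n=100 will be approached". Section 7 randomises 1:1 at the end of the enrolment visit, so 60 completing baseline means about 60 randomised.

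The next paragraph of section 9, on the interviews, says "we anticipate at least an 80% retention rate at 6 months postpartum" and applies that rate to up to 30 intervention women, "which equates to an anticipated 24 participants completing in-depth interviews". The rate is not applied to the power statement.

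The Protocol Summary of the same version (5.0, November 2021) says "Sample size for RCT: 62 participants consented; 43 randomized". It also keeps N=60 under Aim 2 and dates the RCT from April 2021 to December 2022. Nothing says whether 43 is final.

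**The concern.** A reader of section 9 takes away 98% power for a large effect. That figure belongs to 60 women who all supply follow-up data, whereas the current text reports 43 randomised and expects some loss. Self-reported adherence, the outcome on which the calculation adjusts for baseline, is collected only at study visits ("At each study measurement visit, a trained interviewer will administer questionnaire-based measures using paper and pencil"), so missed visits reduce its sample directly. Without the correlations, nobody can check the figures or carry them to another sample size.

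The stated product of the pilot is an effect size for planning a larger trial. No precision is given for it, and a planner who trusts the section 9 figures would think the estimate firmer than it is. The 60 also carries into Aim 3, where the expected number of interviews is derived from 30 women in the intervention arm.

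**Working it through.** **Inputs.** From section 9: N = 60, alpha 0.05, d = 0.30, 0.50 and 0.80, and retention of at least 80%. From section 7: 1:1 allocation. From the Protocol Summary: 43 randomised. Assumed, because not stated: a two-sided test and a 22/21 split of the 43.

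**Formula.** Noncentral t with N − 2 degrees of freedom and noncentrality d / √(f × (1/n1 + 1/n2)). The factor f is the reduction in variance from baseline adjustment and two follow-ups; f = 1 is a plain two-group comparison.

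**Step 1: the plan's own figures at 60.** With f = 1 (30 per arm) power is 21%, 48% and 86%, so the stated figures rely on an unstated f. Factors of about 0.63 to 0.67 bring all three within about 2 points of 29%, 65% and 98%. For example, f = 0.66 and d = 0.50 give a noncentrality of 0.50 / √(0.66 × 2/30) = 2.38 and power of 65%. No one-sided version fits all three.

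Such a factor is plausible. With f = (1 + correlation between follow-ups)/2 − (correlation with baseline)², correlations of 0.5 and 0.3 give 0.75 − 0.09 = 0.66.

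**Step 2: the same factors at other sample sizes.** For 43 women, f = 0.66 and d = 0.50, the noncentrality is 0.50 / √(0.66 × (1/22 + 1/21)) = 2.02 and power is 50%. Over f = 0.63 to 0.67:

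| Women analysed | d = 0.30 | d = 0.50 | d = 0.80 |
|---|---|---|---|
| Stated, 60 | 29% | 65% | 98% |
| Recomputed, 60 (30/30) | 29–30% | 64–67% | 96–97% |
| 48 = 0.80 × 60 (24/24) | 24–25% | 54–57% | 91–93% |
| 43 (22/21) | 22–23% | 50–52% | 88–90% |
| 34 ≈ 0.80 × 43 (17/17) | 18–19% | 41–43% | 79–81% |

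The rows for 48 and 34 are lower bounds: retention is given as at least 80%, and the planned GEE would keep 3-month data from women who miss the 6-month visit.

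**Step 3: does the fall depend on the factor?** Hardly, at d = 0.50. At f = 0.44 power falls from 81.9% at 60 to 67.5% at 43; at f = 0.66 it falls from 65.0% to 50.4%. Across that whole range the fall is 14 to 15 points.

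**Step 4: precision.** The expected 95% half-width in SD units is t(0.975, N − 2) × √(f × (1/n1 + 1/n2)). At 43 this is 2.02 × √(0.63 × 0.0931) = 0.49 to 2.02 × √(0.67 × 0.0931) = 0.50.

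Section 9 also plans point-biserial correlations. Near zero, the half-width is tanh(1.96/√(N − 3)) = tanh(1.96/√40) = 0.30 at 43. For comparison, d = 0.50 corresponds to r = 0.5/√(0.25 + 4) = 0.24.

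**Step 5: interviews.** Section 9 has 0.80 × 30 = 24. With 43 randomised 1:1, the intervention arm has about 21 or 22 women, fewer than 24 even with no loss. At 80%, 0.80 × 21 = 16.8 and 0.80 × 22 = 17.6, so about 17.

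**The case against.** The power paragraph is a prospective rationale for a target of 60 and claims nothing about 43. The version is dated about a year before the end of the RCT timeline, so 43 may be an interim count. The primary hypothesis is feasibility, no go/no-go rule depends on power, and the paragraph already admits low power for small and moderate effects. All of this stands and limits the weight of the point. It does not cover the unqualified 98% for a large effect, the missing loss allowance (which matters even at 60), or the absence of any planned precision.

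Three stronger readings are tempting and are not supported.

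- **That 29%, 65% and 98% are miscalculated for 60.** With f = 0.66 the third figure comes out at about 96%, which might look like an inconsistency. The method and software are not stated, and a normal approximation at f = 0.65 gives 30%, 67% and 97%. A gap of a point or two is not evidence of error.
- **That power at 43 could be as high as 24%, 56% and 92%.** This uses f = 0.576, matched to the 98% alone. At 60 it gives 32.5%, 71% and 98%, which does not fit the stated 29% and 65%.
- **That a loss allowance is also owed for viral load because section 3 mentions "HIV viral load using dried blood spots".** Sections 2 and 7 take viral suppression from clinic records, and section 7 expects those for every woman regardless of visit attendance. Which source applies is a separate question, and a calculation on Cohen's d does not describe a binary outcome.

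The interview count has similar limits: section 9 says up to 30, retention may exceed 80%, and section 7 promises extra effort to reach women not retained in the intervention.

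**Conclusion.** The point holds as a gap between the stated power and the numbers in the same version. Section 9 gives power only for 60 women at baseline, with no loss and no correlations, while the Protocol Summary reports 43 randomised. If 43 is final, power is about 22–23%, 50–52% and 88–90% before loss, and no lower than about 18–19%, 41–43% and 79–81% at the plan's own minimum retention. Even at 60, the minimum retention would bring the 98% down to about 91–93%.

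These figures rest on a variance factor inferred from the stated powers, a two-sided 5% test and a near-even split. The sponsor's own correlations could move them, although the fall of 14 to 15 points at d = 0.50 is stable across the factors tried. Severity is minor to modest. A reader might infer that the trial must recruit more women; nothing here supports that, since the pilot does not claim to be a powered test of efficacy.

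**What to change.** - Reconcile 60 with 43 across the Protocol Summary, section 3 and section 9, and say whether 43 is final.
- In section 9, restate the power, above all the 98%, for the number randomised and for the number expected to supply follow-up questionnaire data on self-reported adherence. State the sponsor's own correlations, the sidedness and the retention assumption.
- Report each effect size, including the 6-month point-biserial correlation, with a 95% confidence interval. State the expected half-width: about 0.49–0.50 SD adjusted, and about 0.30 on the correlation scale, at 43.
- If 43 is final, replace the 24 expected interviews with a number the intervention arm can supply, and revisit the saturation statement that rests on it.

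The cost is rewording two paragraphs and reconciling one number. The stated power becomes less favourable. No extra participants, visits or data are needed.

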2. STUDY AIM & OBJECTIVES

Study aim

The objective of this study is to identify how influential factors change during key moments of transition during pregnancy and postpartum and to construct an intervention that effectively addresses these moments of transition to bolster ART adherence for mothers living with HIV.

Study approach

This study includes two phases:

1. A longitudinal qualitative cohort to identify and characterize factors that influence women's adherence behaviors as well as perceptions and motivations for continued treatment and engagement in care and examine participants' preferences of adherence intervention structure and delivery, in order to shape the design components of the bio-behavioral intervention.
2. Conduct an open pilot and small scale RCT of the intervention to determine feasibility, and preliminary efficacy of the intervention to improve ART adherence among pregnant and postpartum women living with HIV and in-depth interviews with intervention participants to determine acceptability and to identify ways to refine the intervention for future evaluation.

Note that Phase 1 received ethical approval from UCT HREC previously (HREC: 344/2017). This protocol focuses on Phase 2 (Aims 2 & 3).

For Phase 2, the key outcomes are:

Primary Outcomes

1. Feasibility: Feasibility will be assessed through the number of counseling sessions completed.
2. Preliminary efficacy - ART Adherence: Preliminary efficacy will be assessed as the correlation between study arm and self-reported HIV adherence on the 3 item Wilson ART adherence scale (self-report, 3 item scale recoded as 0-100, 100 indicating perfect adherence in the past month) at 6 months postpartum.
3. Preliminary efficacy- Retention in HIV services: Preliminary efficacy will be assessed as the correlation between study arm and retention in HIV services at 6 months postpartum. Retention in HIV services is measured by clinic records. Retention at 6 months postpartum is measured as attended HIV clinic appointment in the past 3 months.
4. Preliminary efficacy-viral suppression: Preliminary efficacy will be assessed as the correlation between study arm and viral suppression at 6 months postpartum. Viral suppression will be measured by clinic records, with viral suppression defined as HIV viral load less than 200 copies/mL.

Secondary Outcomes

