Quantitative data will be captured into a custom designed Microsoft Access database. The database will be password-protected following standard password safety procedures, and will be maintained in a firewall-protected UCT server with daily backups. The database will be designed and maintained by the project manager. The study coordinator will direct queries and data

quality assurance (QA)/quality control (QC) activities, and supervise data entry, with oversight from the project manager. Data QA will be in the form of robust database structure and platform, and 'front-end' data checks including real-time database queries. QC will be through data checking scripts to identify out-of-range values, logic violations and missing observations. Queries will be resolved based on reference to the completed questionnaires in question; all data queries and responses will be logged, and edits will be implemented through separate program files.

Qualitative data from IDI will be transcribed verbatim and translated into English. Translations will use unique participant identifiers, not participant names. All electronic files will be encrypted and password protected.

Data analysis

Quantitative data will be exported to Stata Version 14.0 (Stata Corporation, College Station, Texas) for analysis. We will analyze all primary and secondary outcomes preliminarily using simple means and standard deviations and point-biserial correlations to estimate effect sizes where appropriate. For outcomes that are indicative of a possible difference by condition, we will utilize more advanced analytic techniques, i.e generalized estimating equations (GEE), as follows:

To compare the impact of intervention condition on self-reported ART adherence, engagement in ART services and HIV viral suppression, we will utilize a series of generalized estimating equations (GEE) using Poisson distributions where appropriate. Outcome analyses will control for baseline self-reported adherence and any baseline differences on demographic variables. Intervention condition, time of assessment, and condition*time interaction will be entered as model effects. We will use GEEs to predict key psychosocial outcomes (adherence self-efficacy) by intervention condition. If there is evidence of an intervention effect we will explore factors that may modify intervention effects, we will compare intervention effects within subgroups of women based on key demographic clinical and psychosocial characteristics.

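### The 29/65/98% power is quoted for a two-visit, baseline-adjusted model; the primary adherence analysis is a correlation at 6 months, with about 21/48/86% power even if all 60 women are observed

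*Combined protocol and SAP*

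**What the plan says.** Three places in the protocol bear on this.

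- **Section 9, Sample size considerations: pilot study.** Power is stated "With a sample size of 60, between two groups, 2 follow-up measurements, controlling for self-reported baseline adherence", at a 0.05 level: "29% power of finding a small effect" (d = 0.30), then 65% for d = 0.50 and 98% for d = 0.80. No correlation between the two follow-ups, or between baseline and follow-up, is given. The paragraph calls the pilot exploratory and concedes low power for small and moderate effects.
- **Section 2, Primary Outcomes.** "Preliminary efficacy will be assessed as the correlation between study arm and self-reported HIV adherence on the 3 item Wilson ART adherence scale", at 6 months postpartum. Retention and viral suppression are defined the same way, as correlations with arm at 6 months.
- **Section 9, Data analysis.** "We will analyze all primary and secondary outcomes preliminarily using simple means and standard deviations and point-biserial correlations to estimate effect sizes where appropriate". Outcomes that then suggest a difference by condition go on to GEE, which controls for baseline adherence and includes condition, time and their interaction.

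**The concern.** A second follow-up and a baseline covariate both reduce the variance of the arm comparison, and the power paragraph takes credit for both. A point-biserial correlation at one visit has neither: it uses one measurement per woman and no covariate. (The protocol does not use the word unadjusted; that follows from the kind of analysis it names.) So the stated power is not a property of the analysis that defines the primary adherence outcome.

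What is at stake is how the adherence result is read. The plan concedes weakness only for small and moderate effects, which leaves 98% for a large effect as the one reassuring figure. A reader who relies on it would put the chance of missing a large effect at 2%. For the 6-month correlation it is about 14%.

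**Working it through.** **Inputs**

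- N = 60, two groups, level 0.05, and the three effect sizes: section 9, pilot sample size.
- Allocation "using a 1:1 randomization scheme" (section 7, Randomization), so 30 per arm.
- Retention of at least 80% at 6 months: section 9, sample size for the in-depth interviews.
- Assumed here because not stated: two-sided test, equal arms, normally distributed score, and the correlations used below.

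**Step 1. Can the plan's own figures be reproduced?**

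For the average of two follow-ups adjusted for baseline, the variance relative to a single unadjusted visit is v = (1 + ρ)/2 − b², where ρ is the correlation between follow-ups and b that of baseline with each follow-up. Power comes from the non-central t distribution with non-centrality d × √(60/4) / √v.

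| Calculation | d = 0.30 | d = 0.50 | d = 0.80 |
|---|---|---|---|
| Stated in the plan | 29% | 65% | 98% |
| v = 1 (no gain), two-sided | 20.8% | 47.8% | 86.1% |
| v = 1, one-sided | 31.0% | 60.6% | 92.2% |
| 120 observations taken as independent | 37.1% | 77.5% | 99.1% |
| v = 0.66 (e.g. ρ = 0.5, b = 0.3: 0.75 − 0.09) | 29.0% | 64.9% | 96.3% |
| v = 0.60 | 31.4% | 69.1% | 97.6% |

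The 29% and 65% need v of about 0.65 to 0.67. The 98% needs v of about 0.55 to 0.60. These ranges do not overlap, so no single variance factor returns all three after rounding. The stated figures clearly rest on a repeated-measures gain, a covariate gain, or both, but the inputs given do not determine them.

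**Step 2. Power of the 6-month correlation, all 60 observed**

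Testing a point-biserial correlation is equivalent to a two-sample t-test with N − 2 = 58 degrees of freedom. The non-centrality is d × √15, which is 1.16, 1.94 and 3.10. Power is 20.8%, 47.8% and 86.1%. The stated figures are higher by 29 − 20.8 = 8.2, 65 − 47.8 = 17.2 and 98 − 86.1 = 11.9 points.

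**Step 3. At the plan's expected retention**

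0.80 × 60 = 48, or 24 per arm. The non-centrality is d × √12 with 46 degrees of freedom. Power is 17.4%, 39.6% and 77.4%.

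**Step 4. Does the GEE recover the stated power at 6 months?**

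With a condition-by-time term and complete data, the 6-month contrast is not averaged over both visits. It keeps essentially the covariate gain only, v = 1 − b² (57 degrees of freedom).

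| Assumed b | d = 0.30 | d = 0.50 | d = 0.80 |
|---|---|---|---|
| 0.3 | 22.4% | 51.4% | 89.1% |
| 0.5 | 26.1% | 59.4% | 94.0% |
| 0.6 | 29.8% | 66.3% | 96.8% |

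Matching 29% and 65% by the covariate alone needs b of about 0.58. The protocol neither states nor supports such a value.

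**The case against.** The strongest reply is that the plan does contain a model of the kind the power paragraph describes: the baseline-adjusted GEE over both follow-ups. That stands. A reader might infer that the correlation is the only efficacy analysis named, and the documents do not support that. But the GEE is conditional on a first look by correlation, and its interaction term means that a 6-month contrast does not average over visits. The quoted power therefore does not carry over to the primary outcome as defined.

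Second, the first stage estimates effect sizes; it is not a test. A reader might infer from 48% power that a true moderate effect would more likely than not look null at that step and be dropped. The documents do not support that either. They set no p < 0.05 gate, only an unspecified indication of a possible difference.

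Third, the pilot already describes itself as exploratory and underpowered, and its primary hypothesis is feasibility. This also stands, and it limits the consequence. It does not cover the large-effect figure.

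Fourth, the power paragraph does not claim to cover the yes/no outcomes, and section 3 calls adherence the primary outcome with retention and viral load secondary. But section 2 lists retention and viral suppression as primary, so a sentence on scope is useful. It is tempting to supply a binary figure from the 49% disengagement quoted in the Introduction. That is a background figure, not a planning assumption of this trial, and the plan names no target difference, so no such figure belongs in the protocol.

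**Conclusion.** The point holds as a mismatch between the stated power and the analysis that defines the primary adherence outcome. For the 6-month correlation, power is about 21/48/86% with all 60 observed and about 17/40/77% at 80% retention, against 29/65/98% stated. In addition, the stated triple cannot be reproduced from any one set of correlations: the factor that gives 29% and 65% gives about 96%, not 98%.

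These results assume a two-sided 0.05 level, equal arms and a normally distributed score. A one-sided level does not rescue the stated figures (31.0/60.6/92.2%).

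The impact is on interpretation, not on the validity of the trial. For small and moderate effects, underpowered remains the right description. The figure whose meaning changes is d = 0.80: 98% stated, 86% delivered at full follow-up. The Protocol Summary reports 43 women randomized. If all 43 were observed, split 22 and 21 (an assumed split), power would be about 16/36/73%; the mismatch does not depend on that shortfall.

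**What to change.** The power sentence in section 9 is wrong as written for the primary outcome. In that paragraph:

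1. Give power for the 6-month correlation: about 21%, 48% and 86% at N = 60, and the lower values at the number expected to be observed (about 17%, 40% and 77% with 48 women).
2. If a figure for the adjusted two-follow-up model is kept, recompute it, state the assumed correlations, and label it as applying only to the second-stage GEE. Do not simply relabel 29/65/98%.
3. Say that the d-based figures cover the adherence score and not the yes/no outcomes of retention and viral suppression.

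The cost is a few sentences. Design, data collection and analyses do not change; the stated power becomes less favourable.
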